### 13. Changes in the Planned Analysis

[figure not shown]

[figure not shown]

## 15. Appendices

[figure not shown]
### 15.1. Secondary Estimands and Strategies

[figure not shown]

## 15.2. Imputation Algorithm for Partial and Missing Dates and Time

### Medications and Procedures

Impute partial/missing start date with earliest possible date, and end date with latest possible date.

If start date is completely missing in which the day, month, and year are all unknown, then the start date will not be imputed.

For the partial start date,

- If the year is present and the month and day are missing, set month and day to January 1st.
- If the year and month are present and the day is missing and year and month are equal to year and month of first dose, set day to the first dose day.
- If the year and month are present and the day is missing and year and month are not equal to year and month of first dose, set to 1st day of month.

If the end date is completely missing, in which the day, month, and year are all unknown, then the end date will not be imputed.

For the partial end date,

- If the year is present and the month and day are missing, set month and day to December 31st.
- If the year and month are present and the day is missing, set day to last day of the month.

Medications/Procedures with both missing start and end date after imputation will be considered as concomitant.

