5.2.6 Guidance for Overdose

5.3 Concomitant Medication and Dietary Supplements

Any treatment (including nutritional supplements) or procedure administered from the time of consent to the EOS Visit is considered concomitant and will be recorded in the eCRF. This includes permitted medications ongoing at the time of consent. Concomitant medications and procedures are allowed, except for those listed in Section 5.3.2.

Prior medications will not be recorded in the eCRF, except for prior use of systemic corticosteroids, systemic calcineurin inhibitors, and systemic treatment for AD or other indications with an immunosuppressive/immunomodulating substance including (but not limited to) dupilumab, JAKi and aIL13 mABs, with reason for discontinuation recorded where available.

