#### **4.4.5. Pre-specified Subgroups**

The following subgroups will be explored for the primary endpoint and selected key secondary endpoints:

1. Age (<65, >=65)
2. Gender (male, female)
3. Race
4. Region (ASIA-PACIFIC, EMEA, NORTH AMERICA)
5. Weight (<median, >=median)
6. EASI (<=21 vs >21) from eCOA, per baseline definition in Section 4
7. IGA (3 vs 4) from eCOA, per baseline definition in Section 4
8. Previous systemic immunosuppressant use (Yes vs No)
9. Previous biologic use (Yes vs No)
10. Previous dupilumab use (Yes vs No)
11. Previous cyclosporine use (Yes vs No)
12. Previous methotrexate use (Yes vs No)

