## 7. Treatments and Medications

### 7.1. Prior and Concomitant Medications

All medications/vaccinations will be coded according to the World Health Organization drug dictionary (WHODRUG Global B3 March 2021 or later).

Prior medications refer to medications that started any time prior to first dose of study treatment or randomization if that is not available regardless of the end date. AD treatments include systemic and non-systemic corticosteroids, systemic and non-systemic calcineurin inhibitors, and systemic and non-systemic treatment for AD or other indications with an immunosuppressive/immunomodulating substance including (but not limited to) dupilumab, JAKi and aIL13 mABs. Treatments given to AD will be collectively analyzed from all applicable eCRF pages: Concomitant Medications, Prior and Current Systemic and Topical Treatments for AD.

Concomitant medications refer to medications started prior to AND continued after the first dose of study treatment or taken any time after the first dose of study treatment up to the follow-up visit.

The prior and concomitant medications will be summarized separately. At each level of summarization, a patient is counted once if he/she reports one or more medications at that level. Drug class will correspond to the Anatomical Therapeutic Classification (ATC) Level 4 term or other AD-specific, WHODRUG-based classification.

All prior medications will be summarized using counts and percentages.

All concomitant medications will be summarized using counts and percentages for the FAS1 and FAS2 for Part1 study and Part 2 study respectively.

The imputation algorithm for partial and missing medication dates is provided in Appendix 15.2.

All prior and concomitant medications will be presented in a listing.

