All patients should complete the schedule of study visits and assessments whether or not they complete study treatment and whether or not they receive rescue treatment for AD. If a patient has IMP permanently discontinued due to the taking of systemic therapy rescue but consent is retained, study assessments may be continued until Day 169 (Week 24) for patients who discontinue IMP in the first study period, or until Day 365 (Week 52) or the end of the safety follow-up period (whichever is longer) in patients who discontinue IMP after Day 169 (Week 24).

Rescue medication will be coded according to the World Health Organization drug dictionary (Global B3 March 2021 or later). Drug class will correspond to the Anatomical Therapeutic Classification (ATC) Level 4 term or other AD-specific, WHODRUG-based classification. The data will be summarized using counts and percentages by preferred drug name for each treatment group and overall. At each level of summarization, a patient is counted once if the patient reported more than one medication. The analysis will be based on FAS1 & FAS2 for Part 1 and Part 2, respectively.

A listing of rescue medications will be presented.

A blinded medical review of rescue/prohibited treatments will be implemented before or at the time of each database lock by considering the type of medication, indication, timing, frequency and the potential impact of the use of the prohibited medication or procedure on efficacy.

Categorization of medications performed within the frame of this review will be the basis of related intercurrent event determination in line with the estimand strategy in Section 8.

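### SAP 15.2 misdates or misclassifies some medication records: first-dose-month starts are moved to the first-dose day without checking the end date, and undated prior AD treatments become concomitant (minor)

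*SAP*

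**What the plan says.** SAP 15.2, under Medications and Procedures, opens with a general principle: "Impute partial/missing start date with earliest possible date, and end date with latest possible date". The detailed rules follow.

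- A start date with only a year becomes 1 January. A start with year and month becomes the first of the month, with one exception: where "year and month are equal to year and month of first dose, set day to the first dose day".
- An end date with only a year becomes 31 December. An end with year and month becomes the last day of that month.
- A date that is missing altogether, start or end, stays missing.
- Finally, "Medications/Procedures with both missing start and end date after imputation will be considered as concomitant".

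SAP 7.1 supplies the definitions: "Prior medications refer to medications that started any time prior to first dose of study treatment", whatever the end date. Concomitant covers a drug started before first dose and continued after it, or taken at any time after it. The two classes can overlap. SAP 7.1 also says AD treatments are analysed together from the concomitant medication page and the page or pages for prior and current systemic and topical AD treatment, and it refers to 15.2 for missing dates.

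Protocol 5.3 limits what prior treatment is captured: "Prior medications will not be recorded in the eCRF, except for prior use of systemic corticosteroids, systemic calcineurin inhibitors, and systemic treatment for AD". The exception also covers immunosuppressive or immunomodulating treatment given for another indication. The reason for stopping is recorded where available. SAP 7.3 prohibits these classes during the study.

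SAP 7.4 provides for a blinded medical review of rescue and prohibited treatment at each database lock, and states: "Categorization of medications performed within the frame of this review will be the basis of related intercurrent event determination".

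**The concern.** The records most likely to lack dates are past treatments recalled at screening. For systemic drugs, these belong largely to classes prohibited on study. If a date rule labels such a record concomitant, it reads in the tables as prohibited on-study therapy. Pooling the eCRF pages before applying the rule sets aside the page on which the record was entered, which is the best evidence that the course was in the past.

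The first-dose-month rule is a separate problem. It moves a start to Day 1 without looking at the end date, so a treatment washed out in the days before dosing can acquire a start after its own end, or a full on-study span. Topical treatments are pooled as well, so this reaches beyond systemic drugs.

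At stake are the prior, concomitant and prohibited-medication tables and the quality of the dates that the blinded reviewers may be shown.

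**Working it through.** No power or sample-size figure is involved. The check puts missing-date patterns through the 15.2 rules and the 7.1 definitions. The first-dose date of 15 June 2022 is an assumption for illustration. A start on the first-dose day is counted as on-study, and a missing end after such a start is read as continuing.

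| Recorded start | Recorded end | Start after 15.2 | End after 15.2 | Prior? | Concomitant? |
|---|---|---|---|---|---|
| June 2022, no day | 10 June 2022 | 15 June 2022 | 10 June 2022 | No | Start after end; no rule resolves it |
| June 2022, no day | June 2022, no day | 15 June 2022 | 30 June 2022 | No | Yes |
| June 2022, no day | Missing | 15 June 2022 | Missing | No | Yes |
| Missing | Missing | Missing | Missing | Cannot be derived | Yes, by explicit rule |
| Missing | 3 Nov 2021 | Missing | 3 Nov 2021 | No explicit rule; prior by logic | No |
| 2021 only | 2021 only | 1 Jan 2021 | 31 Dec 2021 | Yes | No |
| 2021 only | 2022 only | 1 Jan 2021 | 31 Dec 2022 | Yes | Yes |

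**First-dose month (rows 1 to 3).** The earliest possible date for a June 2022 start is 1 June. The rule gives 15 June, which is 15 − 1 = 14 days later, so the bullet contradicts the general principle above it. In row 1 the treatment demonstrably ended before dosing, so it must have started before dosing, yet it fails the prior definition. In row 2 a treatment that may have stopped before dosing becomes a course from Day 1 to month end.

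The share of day-missing first-dose-month starts that truly preceded dosing depends on the calendar day of first dose. If true starts are spread evenly over a 30-day month (an assumption), the share is (first-dose day − 1)/30:

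- day 1: 0/30 = 0%
- day 15: 14/30 = 47%
- day 30: 29/30 = 97%

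This is a share of such records, not of patients. The documents do not say how many such records exist.

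**Both dates missing (row 4).** The rule ignores the page of origin, so a past systemic course on the prior/current AD treatment page is classed as concomitant.

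**Start missing, end before first dose (row 5).** The start is not imputed and 7.1 defines prior by the start alone, so no rule assigns a class. The course must nevertheless have begun before first dose.

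Row 6 behaves correctly. Row 7 follows the latest-end principle and remains prior, so it loses no history.

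**Comparison within 15.2.** When an adverse event has no onset date but does have an end date, the adverse event rule looks at whether that end falls on or after first dose before calling the event treatment-emergent. The medication rules contain no such check.

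**The case against.** The strongest reply is that none of this need reach the efficacy analysis. SAP 7.4 bases intercurrent events on a blinded medical review of type, indication, timing, frequency and likely impact on efficacy, not on the 15.2 flag. Nothing says that reviewers see imputed dates or are bound by the concomitant default. They may also have the recorded reason for stopping. A reader might infer that undated past therapy turns responders into failures. The documents do not support that: the classification is the reviewers' to make, and the intercurrent-event and estimand tables are redacted. This part of the reply stands. What remains is that timing is one of the review criteria and the SAP does not say how undated or imputed records are presented.

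A reader might also infer that affected patients fall out of the previous-use subgroups in SAP 4.4.5. That is not shown either. The section gives no derivation, concomitant does not exclude prior, and the flags could be taken from the prior/current treatment page whatever the dates.

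It can further be said that exclusion criterion 1 already bars listed treatments before Baseline, which limits first-dose-month records. That is fair, but the washout lengths are not visible, so the remaining frequency cannot be judged. Finally, treating undated records as on-treatment is a common cautious default. That defends it for the concomitant page. It is harder to defend for a page intended to capture earlier treatment.

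The 1 January rule for year-only starts might look as if it hides on-study rescue. It does not do so when the end is on study: such a record is still concomitant under SAP 7.1, and the review considers its indication.

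**Conclusion.** The rules are wrong as written, and the severity is minor. Three faults follow directly from the text:

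- The first-dose-month bullet contradicts the section's own principle and can produce a start after the end.
- The both-dates-missing default overrides the page on which a past treatment was recorded.
- A missing start with a pre-dose end has no stated class.

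The effect falls on the prior, concomitant and prohibited-medication tables. Any effect on intercurrent events runs through the blinded review; its size is unknown and probably small. No effect on the primary result or on the previous-use subgroups is shown. The subgroup finding is limited to this: their derivation is not stated. No figure is put on the number of patients, because the documents give no count of incomplete records. The conclusion assumes that 15.2 is applied to the pooled pages as SAP 7.1 indicates.

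**What to change.** Amend SAP 15.2 and add one line to SAP 4.4.5.

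1. For a start in the first-dose month with no day, use the first-dose day only if the recorded end is known to be on or after first dose, or the end is missing and the drug is recorded as ongoing. Otherwise use the first of the month. Never impute a start later than the end, and state this exception in the general principle. Where start and end both lack a day in that month, the record then counts as both prior and concomitant, in keeping with the earliest-start, latest-end principle.
2. Class any record whose end, imputed if necessary, is before first dose as prior, even when the start is missing.
3. For records on the prior/current AD treatment page or pages with both dates missing, class as prior unless recorded as ongoing. Keep the concomitant default for the concomitant page.
4. Derive the previous-use flags from the prior/current treatment page or pages, irrespective of missing dates.

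Leave the year-only start rule alone. Under Protocol 5.3 the concomitant record also holds drugs ongoing at consent, and moving their starts to first dose would make truly pre-existing drugs non-prior.

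The cost is SAP wording and a few lines of derivation code before lock. Protocol 6.2.4 already collects ongoing status for concomitant medications. Whether the prior/current treatment page has the same field should be checked on the eCRF.

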### Adverse Event

If onset date is completely missing, onset date is set to date of first dose.

If year is present and month and day are missing:

If year = year of first dose, then set month and day to month and day of first dose

If year < year of first dose, then set month and day to December 31st.

If year > year of first dose, then set month and day to January 1st.

If month and year are present and day is missing:

If year = year of first dose and

If month = month of first dose then set day to day of first dose

If month < month of first dose then set day to last day of month

If month > month of first dose then set day to first day of month

If year < year of first dose then set day to last day of month

If year > year of first dose then set day to first day of month

For AEs with completely missing onset date and end date; and for AEs with completely missing onset date and the end date is on or after the first dose of study drug will considered TEAE.

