10.4.2.4.1 Adverse Events

The primary safety endpoint is the incidence of TEAEs.

All AEs in the clinical trial database will be coded according to MedDRA, which will be used to summarise AEs by primary System Organ Class (SOC) and Preferred Term (PT). All AEs will be displayed in listings.

A TEAE is defined as an AE observed starting after the first administration of IMP up until 140 days after the last IMP administration. All TEAEs collected during the main study (to Day 169 [Week 24]) will be summarised. Additionally, all TEAEs collected during the second study period in those patients who achieve ≥ EASI 75 or who attain IGA 0/1 response following 24 weeks of treatment will be summarised (to Day 365 [Week 52]).

Version number: 1

1-Mar-2022

The number and percentage of patients with TEAEs and the number of TEAEs will be summarised in each KY1005 treatment regimen and in the Placebo group.

The number and percentage of patients with TEAEs/AESIs will be further tabulated by causality and severity (mild, moderate and severe) in each KY1005 treatment regime and in the Placebo group.

In addition, the number and percentage of patients with SAEs, TEAEs leading to treatment discontinuation, TEAEs leading to study discontinuation and AEs leading to death will be summarised in each KY1005 treatment regimen and in the Placebo group.

Adverse events will be listed by treatment allocation, grouped by primary SOC and sub-grouped by PT and causality.

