**Pre-treatment AE, treatment-emergent AE, post-treatment AE definition**

The pre-treatment period is defined as the period up to first IMP administration.

The treatment-emergent (TE) period is defined as the period from the first IMP administration to the last IMP administration + 140 days.

The post-treatment period is defined as the period from the end of the treatment-emergent period onwards.

The AEs will be analyzed in the following 3 categories:

Pre-treatment AEs: AEs that developed, worsened, or became serious during the pre-treatment period.

TEAEs: AEs that developed, worsened or became serious during the treatment-emergent period;

Post-treatment AEs: AEs that developed, worsened, or became serious during the post-treatment period.

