**Adverse events will be analyzed as following:**

1. **Pre-treatment AEs summary:** include pre-treatment AEs from on or after screening date to before date of first IMP.
2. **TEAEs summary up to Week 24 (Treatment Period 1):** TEAEs during the period on or after 1st IMP and up to Week 24 visit or with a start date no more than 140 days after last administration of IMP in case of early treatment discontinuation in part 1.
3. **TEAEs summary from Week 24 onwards (Treatment Period 2):** TEAEs during the period from 1st IMP or rerandomization, that is, 1st IMP or rerandomization  $\leq$  start date of AE  $\leq$  Date of last IMP after re-randomization + 140 days;
4. **Overall TEAEs summary (Overall Treatment Period):** Date of First IMP  $\leq$  start date of AE  $\leq$  Date of last IMP + 140 days;
5. **Post-treatment AEs summary:** include post-treatment AEs that occur  $\geq$ 140 days after last IMP.

The incidence of any AEs, TEAEs and serious TEAEs tables will include only one occurrence of a PT per patient. If a patient reports the same PT multiple times, then that PT will only be incremented by one since patient counts will be presented. As with the PT, if a patient reports multiple AEs within the same SOC, then that SOC will only be incremented by one since patient counts will be presented. For tables showing incidence by SOC, PT and severity, SOC will be sorted Internationally Agreed Order. Within each SOC, PTs will be sorted in descending order of frequency on total of all treatment groups.

All AEs in the clinical trial database will be coded according to MedDRA, which will be used to summarise AEs by primary High Level Group Term (HLGT), High Level Term (HLT), System Organ Class (SOC) and Preferred Term (PT). All AEs, TEAEs and serious TEAEs tables will be displayed in listings.

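### SAP 15.2 moves a partial AE onset that matches first dose to the first-dose date without checking the end date, so an event that ended during screening can be counted as a TEAE

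*SAP*

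**What the plan says.** The adverse-event part of SAP 15.2 has two rules for partial onsets that match first dose. With month and year known and the year equal to that of first dose: "If month = month of first dose then set day to day of first dose". With only the year known: "If year = year of first dose, then set month and day to month and day of first dose". Neither carries a condition on the end date.

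The end date appears once in the AE rules, in the closing sentence, which is limited to completely missing onsets: "for AEs with completely missing onset date and the end date is on or after the first dose of study drug will considered TEAE". The first line of the same rules sets a completely missing onset to the first-dose date, also without an end-date condition.

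SAP 9.1 defines the category as "TEAEs: AEs that developed, worsened or became serious during the treatment-emergent period". Its list of AE summaries then works by dates. The overall TEAE summary takes events with a start date from first IMP to 140 days after last IMP, both ends included. The pre-treatment summary is to "include pre-treatment AEs from on or after screening date to before date of first IMP".

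Protocol 10.4.2.4.1 says "A TEAE is defined as an AE observed starting after the first administration of IMP" and also "The primary safety endpoint is the incidence of TEAEs". Protocol 6.4.3 collects AEs from signature of the consent form, so screening events are in the database and pass through these rules.

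**The concern.** Defaulting to first dose is reasonable when the timing of an event is unknown. It is not reasonable when the recorded end date shows that the event was over before any drug was given. In that case the imputed date contradicts the data: the onset falls after the end, and the duration defined in SAP 4.4.6 becomes zero or negative. The event leaves the pre-treatment summary and enters the TEAE tables. The same classification feeds the tables of serious, related and severe TEAEs and of those leading to discontinuation, so one misplaced screening event could appear in any of them.

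**Working it through.** The plan states no figure to reproduce. The check applies the written rules to a worked case and then to a range of dates.

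**Worked case (assumed dates).** First dose 20 June 2022, onset recorded as June 2022, end recorded as 12 June 2022.

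- Month-and-year rule: onset becomes 20 June, 8 days after the recorded end.
- Duration by SAP 4.4.6 (end minus onset plus 1): 12 − 20 + 1 = −7 days.
- Start-date rule in SAP 9.1: 20 June is on or after first IMP, so the event is a TEAE.
- Year-only rule: same result.
- If the onset had been recorded as May 2022, it would become 31 May and correctly stay pre-treatment.

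**Share of month-only screening events affected.** Inputs: screening of up to 28 days (SAP 3.1). Assumed: onset uniform over the 28 days before first dose, and first dose on each day of 2022. An event lasting D days that starts j days before first dose ends before first dose if j ≥ D. That leaves 29 − D onset days, or 365 × (29 − D) cases. It is moved to first dose if onset and first dose fall in the same month.

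| D (days) | cases | moved to first dose | share |
|---|---|---|---|
| 1 | 365 × 28 = 10,220 | 5,348 | 52.3% |
| 3 | 365 × 26 = 9,490 | 4,654 | 49.0% |
| 7 | 365 × 22 = 8,030 | 3,410 | 42.5% |
| 14 | 365 × 15 = 5,475 | 1,695 | 31.0% |

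The count for D = 1 is 7 × 462 for the 31-day months, plus 4 × 434 for the 30-day months, plus 378 for February: 3,234 + 1,736 + 378 = 5,348.

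With first doses from 1 December 2021 to 31 March 2023 instead, the shares are 52.3%, 49.0%, 42.4% and 30.9%. For year-only onsets in 2022 the share is 94% to 96%. That case is remote, because it needs an unknown onset month but a known end date within a four-week period, so it is left out of the count below.

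**Number of events.** The documents give no frequency for screening AEs that end before dosing or for partial dates. Assumed: 5% to 15% of 350 patients have one such event, and 1% to 3% of these events lack the day.

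- Low: 350 × 0.05 × 0.01 × 0.310 = 0.054 events.
- High: 350 × 0.15 × 0.03 × 0.523 = 0.824 events.
- Per arm (divided by 5): 0.011 to 0.165.
- As a share of 350 patients: 0.015% to 0.235%.

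SAP 9.1 counts a patient once per preferred term and once per system organ class. A misplaced event raises overall TEAE incidence only if that patient has no other TEAE, so the last line is a ceiling on these assumptions.

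**With an end-date check**, the share moved to TEAE is 0% in every scenario, and no imputed onset falls after its end date.

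**The case against.** The strongest defence is that the TEAE definition in SAP 9.1 already excludes these events. An event that ended before first dose cannot have developed, worsened or become serious afterwards, and the dated list could be read as only allocating events already classified. A careful programmer might read it that way. But the list and SAP 15.2 are the operational rules, they work on start dates, and no visible text gives the definition priority over an imputed date.

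The second defence is that a first-dose default is conservative and that data checks and queries (Protocol 13.1 and 13.2) will complete most dates. Both points stand and limit the size. They do not remove the problem for dates that stay partial, which are the dates 15.2 exists to handle. Whether the eCRF accepts a partial AE onset cannot be seen from the documents.

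A reader might infer two stronger points, and the documents support neither.

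- That an event with a known onset month is handled worse than one with no onset date. The closing sentence of 15.2 only implies that an end before first dose means not a TEAE. The first line of the same rules sets completely missing onsets to first dose as well, so under the start-date rule both can go wrong.
- That the safety comparison is tilted towards KY1005. The rule is identical in all five arms and adds TEAEs; it does not hide them.

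**Conclusion.** The point holds as a very small correction. As written, SAP 15.2 together with the start-date rule in SAP 9.1 can classify an event recorded as over before first dose as treatment-emergent, against both documents' definitions. This is a stated rule that gives a wrong result, not a gap in detail. The expected size is under one event in the whole trial, on assumed frequencies. The effect does not depend on arm and runs towards over-counting. It would not change any conclusion about TEAE incidence. The reading of the rule is certain; the event count depends on the assumed event and partial-date rates and on uniform onset and first-dose dates.

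**What to change.** Add to the adverse-event part of SAP 15.2:

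> If the AE end date (complete, or partial but clearly before first dose) precedes the first dose, the AE is classified as pre-treatment and its imputed onset may not be later than the end date, whether onset is partial or completely missing; otherwise the existing rules apply.

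The cost is one sentence and one programming condition on a field that 15.2 already uses. If end dates are correct, no true TEAE is moved, because a TEAE cannot end before first dose. The downside is that a wrongly entered end date could remove a true TEAE, so every record with a partial or missing onset and an end date before first dose should be queried before database lock. An onset and end both recorded only as the month of first dose stays unresolved and remains a TEAE under the existing default, which is acceptable.
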